5.2.3 Missing data

All continuous outcomes: missing follow-up data

For all outcomes, participants with missing data will be excluded from the relevant analysis. This "complete-case analysis" is valid under the assumption that the outcome is missing at random (MAR), conditional on randomised group, baseline value and other covariates in the model.

Demographic characteristics of participants at baseline will be summarised in those with and without data for the primary outcome at 24 weeks.

Primary outcome: sensitivity analyses

A sensitivity analysis will be conducted using a mixed model for repeated measures (MMRM) to account for missing data. Under a MMRM approach, all data (e.g. at both 12 and 24 weeks) contributes to the model and missing values are implicitly handled under the assumption of MAR. For the MMRM analysis, the fixed variables of the analysis model will include randomisation group, timepoint (12 or 24 weeks), group by timepoint interaction, baseline value of the outcome, randomisation stratification variables (sex, ethnicity, background medications) and age as covariates. An unstructured covariance matrix for measurements within the same participant will be used. Post-hoc comparisons at 24 weeks will be extracted and compared to the primary analysis.

A per protocol (PP) analysis will additionally be performed, including participants who have adhered to the intervention as described in section 3.2.

5.2.6 Subgroup analyses for primary outcome

For the primary outcome only, interactions between randomised group and (1) sex (men/women), (2) age (<70 years) ≥70 years), and (3) functional status (SPPB ≥10 vs SPPB <10) will be tested by including the relevant interaction parameters in the analysis model and performing an F-test of the null hypothesis that these parameters are 0 (i.e. no significant interaction).

If the p-value for any of the interactions tested above is <0.05, then estimates and 97.5% confidence intervals of the 2 intervention effects (DAPA vs DIET-CONT, DAPA+EX vs DIET-CONT) on the primary outcome will be reported within the relevant subgroups, based on fitting the linear regression model described in section 5.2.2 within each subgroup. For example, if the p-value for the randomised group x sex interaction is <0.05, then the primary outcome results will be presented separately within men and women.

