5.2 Analysis methods

5.2.1 Deviations from the published protocol

A brief analysis plan was reported in the published protocol (Sargeant et al. 2024). The analysis plan described below is intended to supersede the published protocol. In particular, greater detail is provided on the sub-group analysis and missing data. The order of outcomes has been rearranged (as described in section 5.1.2). Select outcomes (MRI- derived intra- and inter-organ adiposity, cardiac strain parameters and aortic distensibility) that were described in the study protocol and/or trial registries but are omitted from this SAP. This is to avoid multiplicity in secondary outcomes and retain a focus on clinical parameters linked to the primary outcome. Additional exploratory outcomes will be saved for sub-analyses. We have also revised the stratification criteria for age (from 65 years to 70 years) to reflect older than anticipated population at recruitment with functional status also added as a stratification factor for the sensitivity analysis, reflecting the focus of the trial and primary outcome.

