5.2.2 Analysis of the primary and secondary outcomes

Primary outcome

The mean and SD of mPPT will be calculated at baseline, by randomised group. Mean and SD of the change values will be reported between baseline and 12 weeks and between baseline and 24 weeks. The outcome at 24 weeks is primary.

For the primary outcome, the 97.5% confidence intervals and p-values for the comparison of each intervention group with the control group will be derived from a linear regression model with change in

mPPT as the dependant variable and randomisation group included as a fixed factor. Baseline mPPT value, randomisation stratification variables (sex, ethnicity, background medications) and age will be included as covariates. It is anticipated the primary outcome will be normally distributed. This will be inspected and alternative distributions will be considered where appropriate. P < 0.025 will be considered significant. The adjusted intervention effect (intervention vs control) will be used to interpret results.

Secondary outcomes

Secondary outcomes that are changes in continuous variables between baseline and either 12 or 24 weeks will be analysed using the same method as the primary outcome. However, secondary outcomes will be reported with 95% confidence intervals. P values will not be reported for secondary outcomes; results for the intervention effect that do not cross the null will interpreted as significant. Binary variables will be analysed using logistic regression.

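### Subgroup effects on mPPT are reported only after an interaction p<0.05, so the subgroup differences that appear are selected for size; the separate refits also do not match the model tested

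*SAP*

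**What the plan says.** SAP 5.2.6 names three factors for the primary outcome: sex, age (below 70 or 70 and over) and functional status (SPPB 10 or more, or below 10). Each group-by-factor interaction is tested by adding interaction parameters to the analysis model and "performing an F-test of the null hypothesis that these parameters are 0". With three arms and a two-level factor, this is a 2-degree-of-freedom test.

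Reporting is conditional: "If the p-value for any of the interactions tested above is <0.05, then estimates and 97.5% confidence intervals of the 2 intervention effects" are given within the relevant subgroups. They come from a separate refit, "based on fitting the linear regression model described in section 5.2.2 within each subgroup". The plan illustrates this with sex: "if the p-value for the randomised group x sex interaction is <0.05, then the primary outcome results will be presented separately within men and women". No other section provides for subgroup effects when the test is not significant.

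SAP 5.2.2 defines the model to be refitted: "Baseline mPPT value, randomisation stratification variables (sex, ethnicity, background medications) and age will be included as covariates". It contains sex and age, but no SPPB term and no age-group term.

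SAP 5.2.1 describes "functional status also added as a stratification factor for the sensitivity analysis". The sensitivity analyses in 3.3 and 5.2.3 are the MMRM and the per-protocol analysis, and neither uses functional status. It appears as an analysis factor only in 5.2.6.

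**The concern.** An estimate shown only when its own test is significant is biased away from zero, and the bias grows as power falls. Interaction tests in a trial sized for a main effect have low power, so the bias here is large. A reader who sees effects for men and women, or for higher and lower SPPB, would take the difference as an estimate of effect modification, although it was printed only because it was large. The caution about chance findings in SAP 5.2.8 is written for secondary outcomes and does not cover these analyses.

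Two lesser points follow from the separate refits. The model as defined includes a covariate that does not vary within one sex, so the plan's own example cannot be fitted exactly as written. And the estimates come from a different model from the one that triggered their reporting.

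**Working it through.** **Inputs from the SAP.** 38 completers per arm, target difference 2, SD 2.4, 90% power, alpha 0.025 (2.3); 1:1:1 allocation (2.1); covariates (5.2.2); interaction test and reporting condition (5.2.6).

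**Assumptions not in the SAP.** Subgroup share 50% or 30%; true gap of 0, 1 or 2 units, where the gap is the difference between the two subgroups in the intervention effect; the same gap in both active arms; average effect 2 units in both; residual SD 2.4 after covariates.

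**1. The plan's sample size.** Normal approximation, two-sided alpha 0.025: n = 2 × (2.4/2)² × (2.241 + 1.282)² = 2.88 × 12.41 = 35.7, so 36. The exact t version gives power 0.8997 at 37 and 0.908 at 38. The stated 38 per group is reproduced.

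**2. How often the condition is met.** Let v = 2.4² × (1/n₁ + 1/n₂), with n₁ and n₂ the subgroup sizes within one arm. The gap for one active arm has variance 2v. The two gaps share the control arm and have covariance v, so for an equal gap g in both the noncentrality is λ = 2g²/(3v).

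- 50:50: v = 5.76 × 2/19 = 0.606; SE of a gap = √1.213 = 1.10; λ = 1.10 for g = 1 and 4.40 for g = 2.
- 30:70: v = 5.76 × (1/11.4 + 1/26.6) = 0.722; SE = √1.444 = 1.20; λ = 0.92 and 3.69.

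With 114 participants and 10 coefficients the critical F(2, 104) is 3.08. The pass probabilities are 13.9% and 44.0% (50:50), and 12.4% and 37.7% (30:70).

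**3. What is reported once the condition is met.** Simulation of 10,000 trials per row, with the other covariates in the model and a random subgroup split:

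| Split | True gap | Trials with p<0.05 | Mean gap, all trials | Mean gap, p<0.05 only | Mean absolute gap, p<0.05 only |
|---|---|---|---|---|---|
| 50:50 | 0 | 5.1% | -0.01 | -0.07 | 1.99 |
| 50:50 | 1 | 13.8% | 1.01 | 2.29 | 2.43 |
| 50:50 | 2 | 41.6% | 2.00 | 2.85 | 2.86 |
| 30:70 | 0 | 5.1% | 0.00 | -0.02 | 2.21 |
| 30:70 | 1 | 12.0% | 1.00 | 2.42 | 2.60 |
| 30:70 | 2 | 35.7% | 1.98 | 3.03 | 3.05 |

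The pass rates agree with step 2 to within about 2.5 percentage points. With no true gap and a 50:50 split, the larger subgroup effect shown averages 3.01 and the smaller 1.02, although both are truly 2. Their mean, (3.01 + 1.02)/2 = 2.02, is not materially biased.

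**4. Source of the bias.** Over all trials, the separate fits give mean gaps of 1.01 and 2.00 for true gaps of 1 and 2 (50:50). Among trials with p<0.05, the single interaction model gives the same 2.29 as the separate fits for a true gap of 1. The condition causes the bias; the choice of fit does not.

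**5. Three tests.** If all three interactions are null and independent, at least one reaches p<0.05 with probability 1 - 0.95³ = 14.3%.

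**6. The separate refits.** Within one sex, the 5.2.2 design matrix has 8 columns (intercept, sex, baseline mPPT, age, ethnicity, medication, two group terms) but rank 7. The sex coefficient is not estimable; the two intervention effects are. The SD of the gap is 1.16 from separate fits against 1.14 from one model (50:50), and 1.33 against 1.27 (30:70). The two sets of estimates differ by 0.18 and about 0.27 units on average.

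**The case against.** The condition was fixed in advance and discourages over-reading of small subgroups. That is a reasonable aim, but showing only the significant results does not achieve it: the subgroups that appear are then the exaggerated ones.

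Four stronger readings are tempting, and the SAP does not support them.

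- *That separate regressions inflate the effects.* They do not (step 4). They lose little precision, and letting covariate effects differ by subgroup is a legitimate choice. What stands is that their estimates do not match the tested model.
- *That the sex-specific analysis cannot be done.* Only the sex coefficient is lost. Omitting sex is the one sensible repair and changes no intervention effect. The problem does not arise for age or SPPB.
- *That the interaction tests have the wrong type I error.* Section 5.2.6 speaks only of adding interaction parameters, and the 5.2.2 model has no SPPB term, so a literal coding could absorb SPPB's prognostic effect into the test. But the stated null is no interaction, ordinary coding adds the main effect, and the test then rejects at about 5%. The sex main effect is already in the model, and continuous age covers part of the age factor. For SPPB, the size of the risk depends on an assumed shift that remains after adjustment for baseline mPPT, which the SAP does not give. It is a reason to name the main effect, not evidence of a wrong test.
- *That real subgroup differences will be hidden.* Low interaction power comes from 38 per arm, and no reporting rule cures it. The SAP does not say that interaction p-values will be withheld; only the within-subgroup estimates are conditional.

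**Conclusion.** The point holds for the reporting condition. For a true 1-unit gap and a 50:50 split, about 13% to 14% of trials would show subgroup effects, and the gap shown would average about 2.3 units, against about 1.0 if always reported. With no true gap, the gap shown averages about 2 units in absolute size. The gap and the larger subgroup effect are inflated, and the smaller effect is pulled down.

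These figures rest on the SAP's 38 per arm and SD 2.4 and on the assumed splits and gaps. A smaller residual SD after covariate adjustment would raise the pass rates and reduce the inflation. The constant sex covariate and the mismatch with the tested model are real but minor. The label in 5.2.1 is editorial. A reader might infer that the trial's main result is affected; it is not, because the primary analysis, its intervals and its error rate do not depend on 5.2.6. The change should be made before the analysis, but the point concerns subgroup reporting only.

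**What to change.** Replace the reporting rule in SAP 5.2.6 along these lines:

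- For each of sex, age (<70/≥70) and baseline SPPB (≥10/<10), fit one linear model on all participants in the primary analysis: the 5.2.2 covariates, the subgroup main effect and the group-by-subgroup interaction.
- From that model, report both intervention effects in each subgroup with 97.5% confidence intervals, together with the 2-degree-of-freedom interaction p-value, for all three factors whatever the result.
- Label these analyses exploratory.
- Delete the p<0.05 condition and the separate within-subgroup fits.

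This removes the selection, deals with the constant sex covariate, makes the estimates consistent with the test, and settles the SPPB coding by naming the main effect. Say that SPPB is the baseline value, since SPPB is also measured at 12 and 24 weeks. In 5.2.1, call functional status a subgroup factor.

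The cost is a few lines of text and code and one forest plot. The downside is that imprecise small-subgroup estimates will always be on view (SE of a gap about 1.1 to 1.2 units from step 2) and must be read with caution.

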5.2.7 Other analyses

For the primary outcome only, if the p-value for either of the 2 intervention effects is <0.025, the effect of DAPA vs DAPA+EX and 97.5% confidence interval will also be estimated for the primary outcome using the same linear regression model described in section 5.2.2. For this scenario, if there is a difference in the intervention effect for primary outcome between DAPA and DAPA+EX, then the secondary outcomes will also be analysed for the same comparison using the approach described in section 5.2.2. This will be considered an exploratory analysis.

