1.3 Primary hypotheses

- H₀: DAPA, alone and in combination with exercise training, will not improve physical function compared with matched diet-induced weight loss.
- H₁: DAPA, alone and in combination with exercise training, will improve physical function compared with matched diet-induced weight loss, with greater improvements in the combined therapy group.

2 Methods

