2.3 Sample size

To detect a clinically meaningful two-unit difference in the primary outcome (mPPT), with an SD of 2.4 units, 90% power and an alpha error rate of 0.025, 38 participants per group were required to complete the trial.

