2.4 Framework

This is a superiority trial. Each of the 2 intervention groups (DAPA and DAPA+EX) will be compared separately to the control group.

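### The DAPA+EX versus DAPA contrast belongs to the primary hypothesis, but its estimate and confidence interval are produced only if a test of a different contrast is significant

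*SAP*

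**What the plan says.** SAP section 1.3, under its primary hypotheses, states that DAPA alone and with exercise will improve function compared with diet-induced weight loss, "with greater improvements in the combined therapy group". That last clause compares DAPA+EX with DAPA.

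Section 2.4 sets out only comparisons with control: "Each of the 2 intervention groups (DAPA and DAPA+EX) will be compared separately to the control group". Sections 3.1 and 5.2.8 likewise count two primary comparisons.

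Section 5.2.7 deals with the remaining contrast through two successive conditions:

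- For the primary outcome, it is estimated with a 97.5% interval "if the p-value for either of the 2 intervention effects is <0.025, the effect of DAPA vs DAPA+EX" being the contrast concerned.
- The same contrast is then carried to the other endpoints on a further condition: "if there is a difference in the intervention effect for primary outcome between DAPA and DAPA+EX, then the secondary outcomes will also be analysed". No criterion for a difference is given.

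The section closes with "This will be considered an exploratory analysis". It is not clear whether this covers the whole section or only the secondary-outcome step. The SAP does not say what happens to the contrast when the first condition fails.

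**The concern.** In this three-arm design, DAPA+EX minus DAPA is the only contrast that isolates the addition of exercise. The condition that releases it tests something else, namely whether either arm differs from diet. Two consequences follow.

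- **Availability depends on the results.** DAPA+EX can be clearly better than DAPA while neither arm separates from DIET-CON, most obviously when the two arms lie on either side of it.
- **The reported estimate is selected.** The DAPA+EX mean enters both the condition and the contrast, so trials in which it happens to be high are the ones more likely to report the contrast. If DAPA+EX is truly the better arm, the reported difference is on average too large.

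The SAP also gives the same question two ranks: part of a primary hypothesis in section 1.3, and conditional and apparently exploratory in section 5.2.7.

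**Working it through.** **Inputs from SAP section 2.3.** A two-unit difference in mPPT, "with an SD of 2.4 units, 90% power and an alpha error rate of 0.025", and 38 completers per group. Sidedness is not stated.

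**Reproducing the sample size.** The normal approximation, two-sided at 0.025, gives n = 2(z₀.₉₈₇₅ + z₀.₉₀)² × SD² / δ² = 2 × (2.241 + 1.282)² × 2.4² / 2² = 35.7, so 36. With the two-sample t distribution, power is 0.8997 at 37 and 0.908 at 38, so 38 is the first number to reach 90%. One-sided 0.025 gives 31 and does not reproduce. I therefore take 0.025 as two-sided.

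**What the condition requires.** The standard error of any pairwise difference is 2.4 × √(2/38) = 0.551. With pooled variance on 3 × 38 − 3 = 111 degrees of freedom the critical value is 2.272, so an observed difference must exceed about 2.272 × 0.551 = 1.25 units. Observed effects of −0.8 and +0.8 versus diet would both miss this, yet the arms would differ by 1.6, which exceeds it. The contrast would not be estimated.

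**Simulation.** Three arms, 38 per arm, SD 2.4, pooled variance, two-sided 0.025, 1,000,000 trials per scenario. The true effects are assumptions; the SAP gives only the 2-unit design difference. Covariate adjustment is not modelled, so 2.4 stands for the residual SD; a smaller residual SD would release the contrast more often.

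| True effects vs diet (DAPA, DAPA+EX) | Contrast not estimated | Mean when estimated / truth | Coverage of 97.5% CI when estimated | Contrast significant but not estimated |
|---|---|---|---|---|
| (2, 3) | 0.1% | 1.00 / 1.00 | 97.5% | 0.0% |
| (1, 2) | 8% | 1.04 / 1.00 | 97.5% | 0.5% |
| (0, 2) | 8% | 2.05 / 2.00 | 97.9% | 5.5% |
| (0.5, 1.5) | 32% | 1.13 / 1.00 | 97.3% | 4.2% |
| (0, 1) | 66% | 1.30 / 1.00 | 96.0% | 13.7% |
| (−1, 1) | 39% | 2.25 / 2.00 | 97.8% | 31.5% |

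The last column is a share of all trials. If the contrast is always estimated, it is available in 100% of trials, without bias and with 97.5% coverage, in every row.

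**The second condition.** Section 5.2.7 does not define a difference. If it meant p<0.025, the chance of meeting it once the first condition is met would be 35% at (1, 2) and 42% at (0.5, 1.5). Both conditions would then be met in 0.917 × 0.352 = 32% and 0.681 × 0.421 = 29% of trials. At (0, 2), where the true difference is 2 units, the conditional chance is 93%. These figures depend on a criterion that the SAP does not state.

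**The case against.** A reader might infer that the trial could end with nothing on DAPA+EX versus DAPA. The SAP does not support that. Section 5.2.2 always reports both adjusted effects against the same control from one model, so their difference is the adjusted contrast. With equal groups, its interval is also roughly as wide as the two that are reported. What is withheld is the formal contrast and its exact interval, which needs the covariance of the two effects.

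A reader might also infer that a primary comparison is compromised. It is not: sections 2.4, 3.1 and 5.2.8 consistently name two, and this rule touches neither. The null hypothesis in section 1.3 contains no DAPA+EX versus DAPA statement; only the closing clause of the alternative does.

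The rule is prespecified, and as a condition for a significance claim it is defensible: if no arm differs from diet, it is met in only 4.6% of trials. The distortion is small if an arm truly has the 2-unit design effect, and coverage stays close to nominal in most scenarios shown. The sharpest loss, at (−1, 1), requires DAPA to be worse than diet.

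Finally, sections 5.2.1 and 5.2.8 aim to contain multiplicity, and a third contrast on every secondary outcome works against that.

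All of this stands, and it limits the severity. It does not justify making the estimate and interval, as distinct from a claim, depend on another test.

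**Conclusion.** The point holds at moderate severity. The SAP places a DAPA+EX versus DAPA statement among its primary hypotheses, yet provides the formal contrast and interval only after a significant result on a different contrast.

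The harm is small when at least one arm has the 2-unit design effect (unestimated in at most about 8% of trials, mean off by about 0.05 units or less). It becomes material when effects are smaller or of opposite sign: 32% to 66% unestimated in the scenarios examined, with an upward shift of 0.13 to 0.30 units. These figures rest on 38 completers per arm, a residual SD of 2.4, two-sided 0.025 and assumed true effects.

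It would be tempting to add that a true 1-unit exercise benefit will usually leave the secondary outcomes unanalysed for this contrast. That follows only if a difference means p<0.025. What the text supports is that the trigger is undefined, so whether it has been met could be decided after the result is seen. Nor do the documents support a requirement to report the third contrast for every secondary outcome.

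**What to change.** 1. In section 5.2.7, estimate DAPA+EX minus DAPA for the primary outcome, with its 97.5% confidence interval, from the section 5.2.2 model whatever the comparisons with control show. If a condition at p<0.025 is wanted, let it govern only whether significance may be claimed.
2. Reconcile section 1.3 with section 5.2.7: either list the contrast as a secondary comparison, or remove the clause on greater improvement from the alternative hypothesis. State what the exploratory label covers.
3. Do not let the undefined trigger decide whether the contrast is analysed for secondary outcomes. Preferable, but optional, is to report it with confidence intervals, labelled exploratory, for at least the key secondary outcomes.

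The cost is one more contrast from a model already fitted and slightly more multiplicity, plus extra table entries if item 3 is adopted. No new data or participants are needed. The change should be made before results are seen.
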